# **Structured Protocol**

You are asked to ensure your protocol includes all of the headings listed. If you feel the heading is not relevant to your protocol, then please specify the reason.

**Title of project:** The effect of consuming grass finished lamb meat on omega-3 blood response among healthy consumers

## Aims and objectives

**Overall aim:** To investigate the impact of consuming grass finished lamb meat on human health parameters when compared to concentrate finished lamb meat.

**Primary objective:** To assess the effect of regular consumption of grass finished and concentrate finished lamb meat on the plasma and platelet omega-3 status of healthy individuals.

**Secondary objective:** To assess the effect of consumption of grass finished and concentrate finished lamb meat on cardiovascular risk factors including blood pressure, body mass index (BMI), total cholesterol, HDL-cholesterol and triglycerides among healthy individuals.

### Background

In recent years, consumers have become increasingly interested in the food they eat, given advances in nutrition science, the nutritional quality of food products and knowledge of non-communicable disease aetiology. Currently, cardiovascular disease represents 31% of deaths worldwide (World Health Organisation, 2016) and incidence is predicted to rise given modern day lifestyle habits including smoking, physical inactivity and poor diet. Meat consumption can contribute a nutritionally significant as part of a balanced diet. Due to its high biological value, meat is an important source of nutrients for human health and wellbeing, e.g. iron, vitamin B12 and zinc. However, there are concerns and controversy surrounding the fat content of meat, despite fat being a vital component directly influencing palatability, flavour and overall liking (Font-i-Furnols and Guerrero, 2014). Fat type and content varies greatly between species and is further influenced by age, sex, genetic makeup and nutrition of the animal (Khan et al, 2015; Scollan et al, 2017). Within the muscle, fat is distributed into neutral and polar fractions and deposited intermuscular, intramuscularly or subcutaneously, with type and amount of lipid varying within individual muscles (Listrat et al, 2016).

Date: 22/03/2019

When compared to monogastric meat, ruminant meat contains high levels of saturated fatty acids (SFA) and trans-fatty acids (TFA) relative to monounsaturated fatty acids (MUFA) and polyunsaturated fatty acids (PUFA). However, all meat types are relatively low in the essential omega-3 (*n*-3) fatty acids for which naturally rich sources include fish and fish products. Nonetheless, by nature of its frequent consumption ruminant meat supplies not just dietary SFA but also makes considerable contributions to dietary MUFA and PUFA.

Excessive intake of dietary SFA is known to increase risk of cardiovascular disease (CVD) and contribute to various other non-communicable disease incidence (Mensink, 2005). UK dietary reference values recommend, for adult males and females, total fat intake should not exceed 35% of food energy, with 11% of this accounting for SFA (British Nutrition Foundation, 2018). Recommended intakes of total *cis*-PUFA are 6.5% food energy, of which there should be a minimum n-3 PUFA intake of 0.2% of food energy (British Nutrition Foundation, 2018). Similarly, The WHO (WHO, 2016) recommended that, for adults, total fat should not exceed 30% of total energy intake. More specifically, total SFA and TFA content should be no greater than 10% and 1% of total energy intake, respectively. The WHO guidelines also recommend that total PUFA should reach 11% of total energy intake with 2% and 9% accounting for *n*-3 and *n*-6 PUFA, respectively.

Despite these guidelines, global *n*-3 intake is sub-optimal, with western countries falling particularly short of optimal blood eicosapentaenoic (EPA; 20:5 *n*-3) and docosahexaenoic acid (DHA; 22:6 *n*-3; Stark et al. 2016). The European Food Safety Authority (EFSA; 2009) stated that for food products to be considered 'a source of' or 'high in' *n*-3 long chain PUFA (LC-PUFA) it must contain per 100 kcal 40 and 80 mg/ day of 20:5 *n*-3 and 22:6 *n*-3, respectively. In order to reach the recommended *n*-3 PUFA intake, UK guidelines suggest that two portions of fish per week should be consumed, one if which is oily. However, global fish consumption is lower than recommended, whilst poultry and red meat consumption is higher and represents a large proportion of fat intake.

The relationship between *n*-3 PUFAs and human health is well established and generally accepted. Increased dietary levels of 20:5 *n*-3 and 22:6 *n*-3 have been documented to instigate physiological reaction cascades, thereby improving the inflammatory response, including alleviating arthritis and asthma symptoms (Yashodhara et al, 2009; Norling and Perretti, 2013; Li, 2015). Similarly, enhanced 20:5 *n*-3 and 22:6 *n*-3 has also demonstrated its ability to decrease CVD risk by reducing triglycerides in the bloodstream, lowering the risk of myocardial

Date: 22/03/2019

infarction, stroke, atherosclerosis development and overall risk of death (Jacobson et al. 2012; Givens, 2015; Singh et al. 2016). Nevertheless, there is a level of controversy surrounding n-3 PUFA exhibiting health promoting effects, with some studies finding little or no evidence of significant health benefits of consuming n-3 PUFA (Rangel-Huerta and Gil, 2018). Discrepancies could be explained partially by differences of bioavailability of n-3 PUFA between dietary sources found within foodstuffs and supplementary sources of n-3 PUFA (Harris et al, 2017).

Due to the generally accepted ability of *n*-3 to reduce non-communicable disease incidence, nutritional approaches have focused on increasing the amount of beneficial fats in meat and meat products with emphasis placed on increasing *n*-3 and specifically *n*-3 LC-PUFA. Improving the lipid composition of poultry and monogastric meat has been largely successful. However, the process for ruminant animals is more multifaceted due to the diversity of the rumen and resident microbial community. Consequently, large proportions of dietary PUFA are converted into SFA such as stearic acid (C18:0) or palmitic acid (C16:0) by lipolysis and biohydrogenation processes, which are controlled by complex microbial flora (Lourenco et al. 2010). Research has attempted to overcome the biochemical limitations of nutritionally enhancing ruminant meat by examining early life feeding, including microbial programming (De Barbieri et al. 2015) and finishing feed (Vestergaard et al. 2000). Emphasis has also been placed on the positive benefits of pasture *vs* concentrate feeding.

It is widely accepted that pasture compared to concentrate based feeding is more efficient in enhancing beneficial *n*-3 PUFA in meat of ruminant animals (Nuernberg et al. 2005; Fisher et al. 2010; Hajj et al. 2016; Scollan et al. 2017), with enrichment proving more efficient in lamb than beef (Bessa et al. 2015). More specifically, grass chloroplasts are rich in 18:3 n-3, which are a known precursor for longer chain n-3s such as 20:5 n-3, 22:5 n-3 and 22:6 n-3. In fresh grass, 18:3 n-3 can represent up to 75% of the total lipid fraction (Blasko et al, 2010). This level can be influenced by season, species, geographical location, growth stage, nitrogen fertilization and senescence. In addition, pasture-based feeding provides increased concentrations of vitamin E, which contains valuable antioxidant properties, reducing the incidence of lipid oxidation and therefore minimising the opportunity for skewed flavours and odours to develop.

The effect of animal-based foods enriched fatty acid profiles on human health has received relatively little attention and is largely unknown. In recent years, a single study explored the effect of consumption of either *n*-3 enriched pasture-based feeding or concentrate fed beef and

Date: 22/03/2019

lamb on blood fatty acid profiles and circulatory parameters including blood pressure and cholesterol in an intervention trial among healthy individuals (McAfee et al. 2011). Results showed that the total PUFA and LC-PUFA plasma and platelet lipid composition of individual's subject to the pasture fed meat treatment was significantly higher, when compared to subjects who consumed concentrate fed meat. These results highlight the ability of *n*-3 within enriched meat to be successfully taken up and utilised within the human body. However, this study is an isolated examination of the human health effects of *n*-3 enriched ruminant meat products and further and more in-depth research is required to fully establish a confirmed biological effect and contribute to the current limited literature.

The research area of enriching n-3 PUFA concentration in ruminant meat is increasingly being developed and continues to expand. However, there is a significant lack of research demonstrating the effect of consuming grass finished lamb on n-3 blood status among free living healthy consumers. Therefore, identification of current knowledge gaps is an imperative to overcome the challenges in ensuring an optimal level of n-3 PUFA is present in muscle and in turn consumed by the public, ultimately contributing to human health by assisting with reducing cardiovascular and other non-communicable diseases incidences with little change to customary dietary habits. The present study proposal uniquely focuses on the consumption of lamb meat for a four-week period as a proof of principle technique to demonstrate preliminary biological effect of habitual lamb consumption on blood omega-3 status and cardiovascular risk factors.

## Plan of investigation

### Study design

The study period will consist of a four-week, single blinded, randomised dietary intervention whereby participants will be required to eat three portions per week of lamb meat from one of two treatments for a four-week study period. The study will focus entirely on the consumption of lamb meat. This is because evidence in current literature suggests that lamb muscle has a higher capacity to store omega-3 in the muscle phospholipids when compared to other meats such as beef or pork (Bessa et al, 2015). Therefore, as a proof of principle study, volunteers will consume three portions of lamb per week for four weeks, substituting lamb for regular red meat consumption and therefore maintaining intakes of red meat within safe levels and not encouraging any adverse dietary pattern.

Date: 22/03/2019

Lamb portions will include per week one portion of mince (raw weight 250g) and two portions of lamb chops (raw muscle weight 235g). Raw lamb portions will total 720g per week. Literature suggests cooking losses will represent approximately 32% (Matthew and Garrison, 1975), meaning around 490g of lamb per week will be consumed, keeping below recommendations by the World Cancer Research Fund (WCRF) to consume less than 500g of red meat/week and UK NHS recommendations to consume no more than 70g/day of red and processed meat. One group of participants will receive lamb meat from concentrate finished lambs and another group will receive lamb meat from grass finished lambs. The study will be single blinded meaning researchers will know what treatment participants are receiving however participants will not be told what dietary treatment they are receiving.

Meat will be stored at AFBI Newforge, AFBI Stormont and North South Retail Belfast. The meat will be delivered to the participant's residence frozen on a weekly basis. Days and times of delivery will be discussed and decided on an individual participant basis. Participants will also be expected to keep a three-day food diary which will be completed prior to the intervention start and then again during the mid-point of the intervention during week one and week three. This is where all food and drinks for the three days will be recorded with as much detail as possible regarding consumption (including left overs), time of day, quantity of food and cooking methods. In addition, participants will also be asked to keep a meat diary for the entire duration of the study as a record of whether all meat is consumed or whether some is not consumed. This will also include what cooking methods are used and whether participants consume the subcutaneous fat or not. Participants will receive recipe cards at the beginning of the four-week study period to provide cooking ideas; however, there is no obligation to follow the recipes. Participants may cook the lamb however they choose but will be reminded of the importance of following good food safety and hygiene practices e.g. defrosting meat safely and the importance of thoroughly cooking minced meat.

#### Meat source

The lambs which will provide the meat were reared for an 11-week finishing period at AFBI, Hillsborough, NI. The finishing period started 04th September 2018 and finished on 20th November 2018. The lambs were transported to Dunbia, Dungannon for slaughter on the 21st November 2019. The carcases were left to hang for 48 hours before the meat was processed into loins, shoulder and leg meat. Finer processing including separation of loins into chop

Date: 22/03/2019

portions and mincing of meat was carried out at Loughery College, Cookstown on 26th November 2018 and 16th January 2018, respectively. The loins were band-sawed fresh creating lamp chops, individually packaged and then frozen. The shoulder and leg meat to create mince portions was frozen and then tempered to -1°C, minced, weighed into 250g portions, vacuum packaged and re-frozen. Alternative lambs have been raised and slaughtered to act as a back-up option if any of the intervention study meat was to be unsuitable. A representative proportion of the meat from both the loins and the mince portions will undergo microbial analysis prior to being used in the intervention study.

### Sample size and justification

Healthy volunteers (N=38) will be recruited and allocated to one of two treatments (n=19/treatment) balanced for age and gender using a computer-generated randomization tool, which will be completed with the assistance of [name] (statistician). Sample size was determined using power calculations based on changed in blood plasma and platelet PUFA levels from a similar study (McAfee et al, 2011). Based upon the SD of plasma PUFA of 2 units (%), with 16 in each treatment there will be over 80% power to detect, as statistically significant at the 5% levels, a difference in mean PUFA of 2 units in the grass-fed lamb meat group and the concentrate fed lamb meat group. This will be determined using an independent samples t-test. This difference in plasma PUFA is similar (slightly less than) the difference seen in the previous study (McAfee et al. 2011), however it is anticipated a larger difference will be detected as only lamb meat is being used which is documented to be of increased capacity to store omega-3 PUFA (Bessa et al, 2015) and therefore it is expected that this will have a greater influence on blood plasma PUFA status. The power calculation for platelets will be more limited, however, based on the SD of platelet PUFA of 4 units (%), with 16 in each treatment we would have over an 80% power to detect, as statistically significant at the 5% level, a difference of 2 units in the lamb-fed meat group and concentrate fed meat group. In addition to the 32 required participants established by statistical power calculations an additional six participants will be recruited to account for drop out and non-compliance.

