#### Planned statistical analysis of results

The change in each outcome variable will be compared between intervention groups using an independent samples t-test. A significance level of 0.05 will be used to determine statistical differences. Any effect within treatments from baseline to end of intervention will be analysed using a paired t-test. A significance level of 0.05 will be used to determined statistical differences. All statistical analysis will be carried out with the assistance of [name] and using established statistical software such as SPSS.

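### Allocation is balanced for age and gender but the planned t-test on change ignores both; if either predicts the change, the test is valid but conservative and forgoes some power

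*Combined protocol and SAP*

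**What the plan says.** Sample size and justification states that the 38 volunteers, 19 per treatment, are to be "balanced for age and gender using a computer-generated randomization tool". It does not say how balance is achieved (stratified blocks, minimisation or another method) or how age is grouped.

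The same section sizes the trial on an unadjusted comparison: "Based upon the SD of plasma PUFA of 2 units (%), with 16 in each treatment there will be over 80% power" to detect "a difference in mean PUFA of 2 units in the grass-fed lamb meat group" compared with the concentrate group, and "This will be determined using an independent samples t-test".

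Planned statistical analysis of results gives the whole analysis: "The change in each outcome variable will be compared between intervention groups using an independent samples t-test", with paired t-tests within each group. On the threshold it says "A significance level of 0.05 will be used to determine statistical differences". Age, gender, strata and covariates are not mentioned in that section, and no other section plans an adjustment.

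**The concern.** Balancing on a factor removes that factor's variation from the difference between the group means. An unadjusted t-test still counts the variation within each group as random error. Its standard error then describes simple randomisation, which is not the design used. If the balanced factors predict the outcome, the reported standard error exceeds the true one, the confidence interval is wider than it need be, and the type I error falls below the nominal 5%.

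The trial is small and has no power to spare at its stated analysable size. It takes the trouble to balance at allocation, and the analysis as written does not collect the benefit. At stake is efficiency, not the validity of the result.

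**Working it through.** **Inputs from the documents.** Sample size and justification gives 16 analysable per group, SD 2, difference 2 and the 5% level. Two-sided testing is assumed, because sidedness is not stated. The SD of 2 is taken to apply to the analysed outcome, the change.

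**Input not in the documents.** R² is the share of variance in the change that age and gender explain together. It is assumed at 0, 5%, 10% and 20%.

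**1. The plan's own figure.** n per group = 2(1.960 + 0.842)² × SD²/difference² = 2 × 7.85 × 4/4 = 15.7, so 16. The standard error is 2 × √(2/16) = 0.707. The standardised difference is 2/0.707 = 2.83, and normal-approximation power is Φ(2.83 − 1.96) = 80.7%. The stated figure is reproduced. The exact noncentral t with 30 degrees of freedom gives 78.1%.

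**2. Standard error when the factors are balanced.** With exact balance the true standard error is 2 × √(1 − R²) × √(2/16), while the t-test reports about 0.707 whatever R² is.

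| R² | True SE | Approximate ratio, 1/√(1 − R²) |
|---|---|---|
| 0 | 0.707 | 1.000 |
| 5% | 0.689 | 1.026 |
| 10% | 0.671 | 1.054 |
| 20% | 0.632 | 1.118 |

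Simulation agrees. The mean reported SE against the actual SE is 0.704 against 0.669 at R² 10%, and 0.706 against 0.632 at R² 20%. The reported SE is thus about 5% and 12% too large.

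**3. Type I error and power under exact balance.** The simulation used 100,000 trials per setting, 16 per group, four equal strata (gender by two age groups) and total SD 2. The adjusted model has treatment, gender and age group, with 32 − 4 = 28 residual degrees of freedom.

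| R² | t-test type I error | Adjusted type I error | t-test power | Adjusted power |
|---|---|---|---|---|
| 0 | 5.1% | 5.0% | 78.3% | 78.1% |
| 5% | 4.4% | 4.9% | 78.4% | 79.8% |
| 10% | 3.9% | 5.0% | 79.2% | 82.2% |
| 20% | 2.7% | 5.0% | 80.0% | 86.1% |

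The noncentral t with 28 degrees of freedom gives adjusted power of 77.9%, 80.0%, 82.1% and 86.3%, in agreement.

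**4. Looser balance.** The documents do not guarantee exact balance among those analysed. An assumed alternative used stratified blocks of four, random stratum sizes and six random dropouts from 38, with 12,000 trials per setting. At R² 20% the t-test's type I error was then about 3.5%. At R² 0 adjustment cost about 0.9 points of power. The power gain from adjusting stayed at about 1, 2.5 and 6 points for R² of 5%, 10% and 20%.

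**The case against.** The strongest case against is that no loss has been shown. The outcome is a change score, so any stable effect of age or gender on the fatty acid level cancels. The factors must predict the four-week change, and nothing in the documents says that they do. At R² of 5% the gain is only 1 to 2 points. This objection stands, and the point is conditional for that reason.

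A reader might infer that the plan's standard errors are definitely overstated. The documents do not support that: at R² of zero there is no inflation at all.

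A reader might also infer that the trial falls short of its planned power because of this mismatch. It does not. The sample size was itself based on an unadjusted t-test, so the two sections agree on the test. The t-test's power does not fall below its R² 0 value of about 78% across the assumed range. What is described is a gain forgone.

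A third tempting inference is that the t-test is invalid. It is not: the estimate is unbiased and the error is in the safe direction. For a proof of principle study, a simple valid test is defensible.

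Finally, staggered starts and the allowance of six for dropout and non-compliance mean exact balance may not survive to analysis. This reduces the conservatism somewhat and raises the cost of adjusting when R² is zero, but it leaves the power gain largely intact.

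**Conclusion.** The mismatch between allocation and analysis is real, and its consequence is conditional and modest. If age and gender explain 5% to 20% of the variance in change, the planned test has a type I error between about 4.4% and 2.7% and gives up about 1 to 6 points of power. If they explain nothing, adjusting costs less than one point. The documents do not show where in that range the trial lies.

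The figures rest on two-sided 5% testing, SD 2 for the change, additive effects of gender and a two-level age factor, and balance that is exact or nearly so. They concern plasma PUFA only. The platelet statement ("based on the SD of platelet PUFA of 4 units (%), with 16 in each treatment we would have over an 80% power" for a difference of 2) is a separate problem: exact power there is about 28%, and adjustment raises it only to about 33% at R² 20%.

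The change is worth making because it is almost free. The analysis as planned would not mislead.

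**What to change.** In Planned statistical analysis of results, make the primary between-group comparison a linear model of the change in each outcome with treatment, gender and age as terms. Enter age in the form used for balancing, and state that form in the plan. Report the adjusted difference with its 95% confidence interval. The unadjusted t-test can stay as a supportive check.

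The cost is a wording change before analysis. Age and gender must be known anyway to balance the allocation, and the software named in the plan fits the model. The two terms use two degrees of freedom (30 down to 28 with 16 per group), and the worst case is about 0.2 to 0.9 points of power if neither factor matters.

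Adding the baseline value of the outcome is a separate, optional improvement. It uses one further degree of freedom and is not covered by the figures here.

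### Platelet PUFA power is about 28%, not over 80%, on the stated SD of 4, 2-unit difference and 16 per arm

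*Combined protocol and SAP*

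**What the plan says.** The primary objective covers the effect of the two types of lamb "on the plasma and platelet omega-3 status of healthy individuals" (Aims and objectives), so platelets stand beside plasma as a primary measure.

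Under Sample size and justification, the calculations are described this way: "Sample size was determined using power calculations based on changed in blood plasma and platelet PUFA levels". Two power statements follow.

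- **Plasma:** "Based upon the SD of plasma PUFA of 2 units (%), with 16 in each treatment there will be over 80% power to detect" a 2-unit difference in mean PUFA at the 5% level.
- **Platelets:** "based on the SD of platelet PUFA of 4 units (%), with 16 in each treatment we would have over an 80% power". The target is again 2 units between the groups, tested at 5%.

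The platelet calculation is introduced as the weaker of the two, but no lower power figure is given. The total follows from 16 per arm: "In addition to the 32 required participants established by statistical power calculations an additional six participants will be recruited", which makes 38, or 19 per arm.

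The planned test is the same for all outcomes: "The change in each outcome variable will be compared between intervention groups using an independent samples t-test" (Planned statistical analysis of results).

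**The concern.** The two statements share the difference (2 units), the arm size (16) and the significance level (5%), but the platelet SD is twice the plasma SD. Doubling the SD halves the standardised difference from 1.0 to 0.5, and power must fall sharply. Two claims of more than 80% could both be true if the plasma calculation had a lot of power to spare. It has none: plasma power comes out at about 80%.

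This sentence is the only justification for 16 per arm for the platelet half of the primary objective. A reader who trusts it could take a non-significant platelet result as evidence against a 2-unit effect, when the comparison may have had little chance of detecting one.

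**Working it through.** **Inputs** (Sample size and justification, unless noted)

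- Platelet SD 4, difference 2; plasma SD 2, difference 2.
- n = 16 per arm for power; 19 per arm recruited.
- Level 5%. Sidedness is not stated, so two-sided is assumed and one-sided is also shown.
- Independent-samples t-test on change (Planned statistical analysis of results).

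**Formula.** Noncentrality = difference / (SD × √(2/n)), with 2n − 2 degrees of freedom. Power comes from the noncentral t distribution.

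**Step 1: reproduce the plasma figure.** Noncentrality = 2 / (2 × √(2/16)) = 2 / 0.707 = 2.83. Power is 80.7% by normal approximation and 78.1% by two-sided t-test. The plasma claim therefore reproduces by normal approximation and falls about 2 points short by the t-test.

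**Step 2: platelets by the same method.** Noncentrality = 2 / (4 × √(2/16)) = 2 / 1.414 = 1.41, below the two-sided 5% critical value of about 2.04 on 30 degrees of freedom.

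| n per arm | Two-sided t | Two-sided normal | One-sided t | One-sided normal |
|---|---|---|---|---|
| 16 | 27.8% | 29.3% | 39.6% | 40.9% |
| 19 | 32.3% | 33.8% | 44.7% | 45.9% |

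A simulation of 100,000 trials at 16 per arm gave 27.9% (two-sided t-test).

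**Step 3: what would give 80% (two-sided t-test)**

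- SD 4 and 2 units: 64 per arm.
- SD 4 and 16 per arm: a difference of 4.1 units (3.7 at 19 per arm).
- 2 units and 16 per arm: an SD of about 1.95 (2.14 at 19 per arm).

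**Step 4: possible misprints.** A 4-unit difference with SD 4, or a 2-unit difference with SD 2, has a standardised difference of 1.0, as for plasma. Power is then 78.1% at 16 per arm (80.7% by normal approximation) and 85.1% at 19 (t-test).

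**Step 5: if SD 4 is for a single measurement.** The SD of change is 4 × √(2(1 − r)), where r is the baseline-to-week-4 correlation. The documents give no r, so these values are assumptions.

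| Assumed r | SD of change | Power, 16 per arm |
|---|---|---|
| 0 | 5.66 | 16% |
| 0.5 | 4.00 | 28% |
| 0.8 | 2.53 | 58% |
| 0.88 | 1.96 | 80% |

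**Step 6: expected precision if SD 4 is for change.** The 95% CI half-width is t(0.975, 2n − 2) × 4 × √(2/n). At 16 per arm this is 2.04 × 1.414 = 2.9 units; at 19 it is 2.03 × 1.298 = 2.6 units. Both exceed the 2-unit target.

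**The case against.** The best defence is that this may be a misprint. If 4 units or SD 2 was intended, power is about 78 to 81% at 16 per arm and 85% at 19, and there is no practical shortfall. That is possible, and it is why the inputs must be checked before the sentence is rewritten. It does not rescue the sentence as printed.

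A second defence is that SD 4 may describe a single measurement, so that a strong correlation would shrink the SD of change. This needs r of about 0.88, which nothing in the documents supports. The section says the calculations were based on changes, and the plasma figure reproduces when its SD is entered directly. Reading SD 4 as the SD of change is therefore the more natural choice.

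A third is that a different test was used. A paired test on all 32 people gives 78.2% two-sided and 86.9% one-sided, but it tests within-person change, whereas the sentence concerns a difference between groups. Reading 32 as the number per arm gives 50.4% two-sided and 63.1% one-sided. The arm size itself is unlikely to be the slip, because 16 per arm agrees with the stated totals of 32 and 38.

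Finally, the protocol calls the study a proof of principle and warns that the platelet calculation is weaker. That caution is fair, but the same sentence still asserts more than 80%.

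One objection does stand. Correcting platelets to about 78% by t-test while leaving plasma above 80% on equivalent inputs would create a new inconsistency.

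**Conclusion.** The platelet power statement is wrong as written and must be corrected. With SD 4 as the SD of the analysed change and a two-sided 5% t-test, power is about 28% at 16 per arm and 32% at 19. A true 2-unit difference would be missed in about 72% of repeats at 16 per arm (100 − 27.8), not in fewer than 20%. The conclusion does not depend on sidedness or on the approximation used: the most favourable between-group figure at 16 per arm is about 41%.

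The documents cannot show which of the SD, the difference or the power is mistaken. The size of the real shortfall depends on that answer; under either misprint it largely disappears. Both power calculations concern total PUFA, so power for platelet omega-3, the outcome in the primary objective, cannot be derived from the documents.

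**What to change.** Keep the sample size. The sponsor should check the source calculation, confirm the platelet SD and difference, and state whether the SD is for change or for a single measurement and whether the test is two-sided. Then correct the sentence. The figures below take the SD as that of change and the test as two-sided.

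- **(a) SD 4 and 2 units stand:** *With SD 4 and 16 per treatment, power is about 28% for a 2-unit difference; 80% power is reached only for about 4.1 units (3.7 with 19 per treatment).*
- **(b) 4 units was meant:** correct the difference and state power as about 78% by t-test (80.7% by normal approximation).
- **(c) SD 2 was meant:** correct the SD and give the same figures for 2 units.

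Under (b) or (c), quote plasma and platelet power by the same method. In every case, report the platelet between-group difference with its 95% CI and say that the calculation is for total PUFA and not omega-3. Making platelets a secondary outcome is optional and not needed for this correction.

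The cost is one check of the inputs and a short rewrite of one section, with a less favourable power figure or a larger detectable difference if SD 4 and 2 units stand. It needs no extra participants and no change to the primary objective.
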